6.2 Schedule of assessments

The assessments to be performed during the study are described in Table 4: Schedule of assessments – the first 14 weeks of the study, Table 5: Schedule of assessments – continued treatment Year 1 and 2 and Table 6: Schedule of assessments – continued treatment Year 3. The procedures are further described in Sections 6.2.1– 6.2.5.

Table 4: Schedule of assessments – the first 14 weeks of the study

Study period:	Screening	Baseline				Treatment						Post-treatment				
Week:	-4 – 0 “0”	1	2	3	4	5	6	7	8	9	10	11	12	13	14	
Clinic visit		1		2		3		4		5		6		7		8
Incl/Excl criteria¹	X				X											
Demographics	X															
Vital signs	X														X	
Physical exam	X				X						X				X	
PH Med History	X															
Medical history	X															
Concomitant med	X		X		X		X		X		X		X		X	
Pregnancy test	X															
Plasma oxalate			X		X		X		X		X		X		X	
Faeces					X							X			X	
Safety Labs²	X				X							X			X	
Treatment						X	X	X	X	X	X					
Adverse events							X		X		X		X		X	
Speckle Tracking Echocardiography	X ³															

1. Eligibility criteria will be evaluated at Screening and after Baseline. A stable dialysis regimen should be maintained for 2 weeks before start of baseline (2 weeks before visit week 2) and during the whole study.

2. Safety labs include: haematology analysis, clinical chemistry analysis and urinalysis and will be analysed at the local lab. Safety labs will be analysed at screening visit and at week 4, 10 and 14 +/- 1 week.

3. Speckle Tracking Echocardiography and traditional echocardiography should be done at screening visit +/- 1 month.

Table 5: Schedule of assessments – continued treatment Year 1 and 2

Study period	Continued treatment Year 1 and 2								
Week	0	4	8	12	16	20	24	28	32 ¹
Clinic visit	9 ²	10 ³	11	12	13	14	15	16	17
Vital signs			X		X		X		X
Physical exam			X		X		X		X
Concomitant med	X	X	X	X	X	X	X	X	X
Plasma oxalate	X	X	X	X	X	X	X	X	X
Faeces			X		X		X		X
Safety Labs ⁴	X	X	X	X	X	X	X	X	X
Pregnancy test ⁵	X						X		
Treatment	X	X	X	X	X	X	X	X	X
Adverse events	X	X	X	X	X	X	X	X	X
Speckle Tracking Echocardiography	(X) ⁶						X ⁷		

¹. Treatment will continue until the patient is transplanted. The maximal length of the continued treatment period will be 36 months. Visit intervals and examinations/samplings will be kept the same throughout the year 1 and 2 of the continued treatment period.

² Visit 9 may coincide with visit 8 for patients continuing on treatment immediately after week 14 visit.

³. Visit 10 will be scheduled 28 days (+/- 3 days) after first day of continued treatment after study week 14.

⁴. Safety labs include: haematology analysis, clinical chemistry analysis and urinalysis and will be analysed at the local lab.

⁵. Pregnancy test will be repeated every 6 months during the continued treatment period.

⁶. For patients who did not have a Speckle Tracking/Traditional Echocardiography performed at screening, an effort will be made to perform this examination before start of continued treatment.

⁷. Speckle Tracking/Traditional Echocardiography will be repeated every 6th month during the continued treatment period in weeks 0, 24, 48, 72 and 104.

Table 6 Schedule of assessments – continued treatment Year 3

Study period	Continued treatment Year 3			
Week	116	128	140	156
Clinic visit	28	29	30	31
Vital signs	X	X	X	X
Physical exam	X	X	X	X
Concomitant med	X	X	X	X
Plasma oxalate	X	X	X	X
Faeces	X	X	X	X
Safety Labs¹	X	X	X	X
Pregnancy test		X		X
Treatment	X	X	X	X
Adverse events	X	X	X	X
Speckle Tracking Echocardiography		X		X

1. Safety labs include: haematology analysis, clinical chemistry analysis and urinalysis and will be analysed at the local lab.

6.2.1 Screening

Patient Information must be given and the Informed Consent form must be signed prior to any study related procedures being performed. The investigator shall list all patients who are considered for participation in the study and who have signed the Informed Consent on a Screening and Inclusion log.

The inclusion and exclusion criteria should be reviewed. Demographics and baseline data will be collected. These include:

- Birthdate, height, weight.
- Physical examination and Vital Signs.
- PH medical history (including diagnosis, historical levels of urinary oxalate, renal function).
- Other medical history, including concurrent illnesses and symptoms.
- Concomitant medication.

The following samples should be taken and sent for analysis:

- Haematology analyses, clinical chemistry analyses and pregnancy test.
- Urine sample for urinalysis, if possible.

The patient should be on a stable dialysis regimen individualised to remove adequate oxalate to minimise the risk for systemic oxalosis for at least two weeks prior to baseline (two weeks before visit week 2). The regimen could be either HD or PD or a combination of HD and PD. The PD regimen (number of days/week, hours per treatment, volume of dialysis buffer) and HD regimen (number of days/week; hours per treatment; blood and dialysate flow rates; and HD membrane) will be maintained unchanged for the duration of the study. This will be monitored and recorded by measuring volume of spent dialysate from HD and PD and quantifying dialysis dose of each HD session in terms of Kt/V measurement using an online clearance monitor.

Speckle Tracking Echocardiography and traditional echocardiography will be performed, if possible, at screening visit (+/- 1 month) or before start of continued treatment period (at visit week 14). Speckle Tracking Echocardiography will then be repeated at week 24 in the continued treatment period and thereafter every 6 months until end of treatment, if possible.

The patient (and parents when applicable) will be instructed how to collect faeces samples, and dates for collection will be scheduled. See section 6.3 for further information on collections at patient's home. For the course of the study, the patient should be instructed to maintain their normal diet and fluid intake as prescribed under their standard clinical care. The patient will be asked to avoid taking ascorbic acid preparations or multivitamin preparations during the study period. The patient will be scheduled for a week 2 visit.

6.2.2 Baseline

During baseline plasma oxalate sampling will be done at week 2 and 4. The blood sample will be taken after two consecutive days of dialysis on the preceding days, but prior to the dialysis session on the day of sampling. The blood sample will be processed at the clinical site and the acidified plasma will be shipped frozen to the central

laboratory (Academical Medical Center, Amsterdam, The Netherlands) for determination of oxalate using the Isotope dilution Gas Chromatography with mass selective detection (GC-MSD). Plasma oxalate will also be determined using the Ion Chromatography method at Bonn University Clinical laboratory, Germany.

Safety labs and faecal testing for *O. formigenes* will be performed in week 4.

The faeces sample will be collected either at patient's home or at the clinic and shipped for analysis at Institut für Mikroökologie, Herborn, Germany.

Any changes in concomitant medication will be recorded in the CRF at visit week 2 and 4. At week 4 each patient's eligibility will be reviewed to assure that no exclusionary conditions have developed since the screening visit. The result from the week 2 plasma oxalate sample (total plasma oxalate) will be reviewed for patient eligibility at this point.

For patients who fail any of the inclusion or exclusion criteria, applicable parts of the CRF should be completed and they should be recorded as screening failures in the Screening and Inclusion log.

After verification of the inclusion and exclusion criteria, the patient will be included in the study to receive study treatment.

At the clinical visit week 4 the patient and/or the parents will be instructed about the administration procedures for the study drug. See section 8.1 regarding dose administration. The patient will be scheduled for clinic visits at week 6, 8, 10, 12 and week 14.

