6.2.5 Continued treatment period

Addendum to the ICF needs to be signed for patients who agree to continue on treatment with study drug after the week 14 visit. During the first 24 months of the continued treatment period the patient will be followed by clinic visits every 4th week and during the last 12 months every third or fourth month, please see Table 5: Schedule of assessments – continued treatment Year 1 and 2 and Table 6 : Continued treatment Year 3. Patients who are already treated in year 3 of continued treatment at the time of implementation of this amendment will continue on the previous monthly visit schedule for year 3.

At the clinic visits, blood samples will be taken, prior to the dialysis session, for plasma oxalate as well as for safety labs. Pregnancy test will be taken at continued treatment week 0 (clinic visit 9) and repeated every 6 months during the continued treatment period, for women of childbearing potential.

Faecal sample will be taken every 8th week for the first 24 months of the continued treatment period and thereafter every 12th or 16th week.

At each clinic visit the patient will be assessed for the presence or absence of Adverse Events and changes in concomitant medications.

The patient will receive a shipment of study drug bi-weekly throughout the treatment period. Remaining study drug/empty vials will be returned to the clinic or site pharmacy at the next clinical visit, or the visit thereafter if new supply has not yet been received by the patient.

Speckle Tracking Echocardiography and traditional echocardiography will be done. If the examination could not be done at screening, an effort will be made to perform the examination before start of continued treatment period (at week 0 of the continued treatment, clinic visit 9). The examination will then be repeated at week 24 in the continued treatment period and thereafter every 6 months until end of treatment.

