7.2 Patient exclusion criteria

7. Inability to swallow size 4 capsules twice daily, or using a gastric tube not suited for administration of size 4 capsules via the tube.
8. Ongoing treatment with immunosuppressive medication.
9. The existence of secondary hyperoxaluria, e.g. hyperoxaluria due to bariatric surgery or chronic gastrointestinal diseases such as cystic fibrosis, chronic inflammatory bowel disease and short-bowel syndrome.
10. Use of antibiotics to which *O. formigenes* is sensitive (see section 8.2.2), including current antibiotic use, or antibiotics use within 14 days of initiating study medication.
11. Current treatment with a separate ascorbic acid preparation. Standard of care vitamin supplement for patients on dialysis are allowed.
12. Pregnancy.
13. Women of childbearing potential who are not using adequate contraceptive precautions. Sexually active females, unless surgically sterile or at least 2 years post-menopausal, must be using a highly effective contraception (including oral, transdermal, injectable, or implanted contraceptives, IUD, abstinence, use of a condom by the sexual partner or sterile sexual partner) for 30 days prior to the first dose of OC5 and must agree to continue using such precautions during the clinical study.

14. Presence of a medical condition that the Principal Investigator considers likely to make the patient susceptible to adverse effect of study treatment or unable to follow study procedures.
15. Participation in any study of an investigational product, biologic, device, or other agent within 30 days prior to the first dose of OC5 or not willing to forego other forms of investigational treatment during this study.

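### The week 4 eligibility review must cover pregnancy (exclusion 12), but no scheduled pregnancy test supports it: the only test before dosing is at screening, 4 to 8 weeks before the first dose

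*Protocol*

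**What the plan says.** **The review.** Protocol section 6.2.2 says of the week 4 visit that "eligibility will be reviewed to assure that no exclusionary conditions have developed since the screening visit". The same section makes verification of the inclusion and exclusion criteria the step that admits a patient to study treatment. Footnote 1 of Protocol Table 4 agrees: "Eligibility criteria will be evaluated at Screening and after Baseline". The inclusion/exclusion row of that table is marked at screening and at week 4.

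**The criterion.** Pregnancy is exclusion 12 in Protocol section 7.2. Exclusion 13 covers contraception, including a requirement "for 30 days prior to the first dose of OC5 and must agree to continue using such precautions during the clinical study".

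**The tests.**
- Screening: section 6.2.1 lists "Haematology analyses, clinical chemistry analyses and pregnancy test" among the samples. The pregnancy-test row of Protocol Table 4 carries a single mark, and so does that of SAP Table 1.
- Week 4: section 6.2.2 says "Safety labs and faecal testing for *O. formigenes* will be performed in week 4". Their content is given under Table 4: "Safety labs include: haematology analysis, clinical chemistry analysis and urinalysis and will be analysed at the local lab". Section 11.6 itemises these panels and includes no pregnancy test.
- Later, and only where the patient is a woman of childbearing potential, section 6.2.5 says "Pregnancy test will be taken at continued treatment week 0 (clinic visit 9) and repeated every 6 months during the continued treatment period".

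**The concern.** A review meant to show that no exclusion has arisen since screening needs some information collected after screening. For several criteria the schedule supplies it. Section 6.2.2 points to the week 2 total plasma oxalate result for the oxalate threshold, and the medication criteria can be read against the concomitant-medication updates at weeks 2 and 4. For pregnancy, the only scheduled test result on file at week 4 is the one from screening, which by construction says nothing about what has happened since.

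The protocol also treats its two treatment starts differently. Before continued treatment it schedules a fresh test, although contraception is already required throughout. Before the first course it does not, and no reason is given.

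At stake are patient safety and the documentation of eligibility. SAP section 6.5.4 plans a listing of pregnancy tests by visit (listing 16.2.8.4). As the schedule stands, that listing would contain no protocol-scheduled week 4 result behind the eligibility confirmation.

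**Working it through.** This is schedule arithmetic. The plan states no figure of its own for these intervals.

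**Inputs**
- Screening visit: week -4 to week 0 (Protocol Table 4).
- First dose: after the week 4 visit, since the first course is study weeks 5 to 10 (section 6.2.3 heading). Taken as week 4.
- End of first course: week 10.
- Continued-treatment week 0 (visit 9): week 14 at the earliest, since visit 9 may coincide with visit 8 (Protocol Table 5, footnote 2).
- Patients treated: 12, of whom 8 continued (section 11.5.1.2, as of September 2019).

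**Interval = later week minus screening week**

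| Interval from the screening test to | Screened at week 0 | Screened at week -4 |
|---|---|---|
| first dose | 4 - 0 = 4 weeks (28 days) | 4 - (-4) = 8 weeks (56 days) |
| end of first course | 10 - 0 = 10 weeks | 10 - (-4) = 14 weeks |
| next scheduled test, earliest | 14 - 0 = 14 weeks | 14 - (-4) = 18 weeks |

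The next scheduled test therefore falls at least 14 - 4 = 10 weeks after the first dose and 14 - 10 = 4 weeks after the first course ends. Patients who did not continue number 12 - 8 = 4. Any woman of childbearing potential among them had no second scheduled test.

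**What is scheduled at week 4 that could bear on exclusion 12**
- Physical examination and the repeat inclusion/exclusion review: yes, but neither is a pregnancy test.
- Haematology and chemistry: no pregnancy test among the listed analytes (section 11.6).
- Urinalysis: protein, glucose and pH only (section 11.6).
- Plasma oxalate, faecal sample and concomitant-medication update: not informative about pregnancy.

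So the review is required, the criterion is within its scope, and no scheduled test informs it.

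**The case against.** The strongest case on the other side is that section 6.2.2 asks for a review, not a laboratory test of every criterion. Exclusions such as immunosuppression, antibiotics and ascorbic acid also have no dedicated week 4 test and are settled from history and medication records. A physical examination is scheduled, and nothing prevents the investigator from asking the patient or ordering an unscheduled test. This stands to the extent that a reader might infer that exclusion 12 cannot be checked at all at week 4. The documents do not support that; they show only that no scheduled test supports the check. The comparison with the medication criteria goes only so far, because those have a scheduled data source at that visit.

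Two other inferences are tempting and should be resisted.

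- *That contraception need not have been in place when the screening test was taken.* Counting only the 30-day clause of exclusion 13, the window opens 56 - 30 = 26 days after the test for a patient screened at week -4, but 30 - 28 = 2 days before it for one screened at week 0. However, exclusion 13 opens with an untimed exclusion of women of childbearing potential who lack adequate contraception, and the criteria are also assessed at screening. On that reading contraception is required from screening. It lowers the chance of pregnancy but does not detect one.
- *That a woman who conceived between screening and week 4 would pass through the whole first course undetected.* Patients are seen at weeks 6, 8 and 10, are asked about health problems at each visit, and are examined at week 10. Detection is not assured, but neither is non-detection.

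The practical objection also stands. Twelve is the top of the planned range of about 6 to 12 patients, all 12 had been treated by September 2019, and one remained in the study. Protocol version 12 is dated October 2019. Section 7.3 allows additional patients at the sponsor's discretion, but none is described.

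**Conclusion.** The point holds as a gap between a required review and the schedule meant to serve it. The week 4 review must establish that no exclusion has developed, pregnancy is an exclusion, and the latest scheduled pregnancy result is 4 to 8 weeks old at first dose. The next is at the earliest 14 to 18 weeks after screening, and only for women of childbearing potential who continue.

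It rests on two readings. First, that the single mark in the pregnancy-test row belongs to screening, which the text of section 6.2.1 supports. Second, that first dosing follows the week 4 visit directly; any delay would lengthen the gap.

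The number of women of childbearing potential is not given, so how many patients are affected is unknown. No efficacy endpoint or analysis depends on it. The matter is worth correcting because the correction is small and concerns patient safety, but its forward reach is limited to any further enrolees.

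**What to change.** Reconcile the pregnancy-test row of Protocol Table 4 and SAP Table 1 with section 6.2.2, so that a scheduled pregnancy result for women of childbearing potential is available to the week 4 eligibility review. The week 4 visit already includes safety labs, so no extra visit is needed.

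For patients already treated, state in the study report whether any pregnancy test was done between screening and the first dose, alongside listing 16.2.8.4.

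The cost is one added test in a subset of any additional patients, an edit to two tables, and a sentence in the report. No dosing or clinical rule is proposed. A further test at week 14 for patients who do not continue does not follow from the week 4 review requirement and is not part of this recommendation.

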6.2.3 Treatment period – the first 6-week treatment period (study week 5-10)

During the initial 6 weeks treatment period, the patient will be followed by clinic visits at week 6, 8 and 10, according to Table 4: Schedule of assessments – the first 14 weeks of the study.

At the clinic visits, a blood sample for plasma oxalate will be taken prior to the dialysis session.

At week 10, faecal sample will be taken as well as safety labs.

At each clinic visit the patient will be assessed for the presence or absence of Adverse Events and changes in concomitant medications.

The patient will receive shipments of study drug bi-weekly at week 4, 6 and 8. Remaining study drug will be returned to the clinic or site pharmacy at clinical visits weeks 6, 8, 10 and 12.

6.2.4 Post treatment period – 4 weeks without study drug (study week 11-14)

During the post-treatment period study visits will take place at week 12 and 14. A blood sample will be taken for determination of plasma oxalate prior to the dialysis session in week 12 and 14.

At week 14 faecal sample will be taken as well as safety labs.

At each clinic visit the patient will be assessed for the presence or absence of Adverse Events and changes in concomitant medications. At the clinical visit week 14 a physical examination including vital signs will be performed.

Adverse Drug Reactions (i.e. AEs that are possibly or probably related to study treatment, see section 11.1), which are unresolved at the time of week 14 clinic visit, should be followed until the event has resolved or, if persistent, has been assessed as “chronic” or “stable” for patients not participating in the continued treatment period.

6.2.5 Continued treatment period

Addendum to the ICF needs to be signed for patients who agree to continue on treatment with study drug after the week 14 visit. During the first 24 months of the continued treatment period the patient will be followed by clinic visits every 4th week and during the last 12 months every third or fourth month, please see Table 5: Schedule of assessments – continued treatment Year 1 and 2 and Table 6 : Continued treatment Year 3. Patients who are already treated in year 3 of continued treatment at the time of implementation of this amendment will continue on the previous monthly visit schedule for year 3.

At the clinic visits, blood samples will be taken, prior to the dialysis session, for plasma oxalate as well as for safety labs. Pregnancy test will be taken at continued treatment week 0 (clinic visit 9) and repeated every 6 months during the continued treatment period, for women of childbearing potential.

Faecal sample will be taken every 8th week for the first 24 months of the continued treatment period and thereafter every 12th or 16th week.

At each clinic visit the patient will be assessed for the presence or absence of Adverse Events and changes in concomitant medications.

The patient will receive a shipment of study drug bi-weekly throughout the treatment period. Remaining study drug/empty vials will be returned to the clinic or site pharmacy at the next clinical visit, or the visit thereafter if new supply has not yet been received by the patient.

Speckle Tracking Echocardiography and traditional echocardiography will be done. If the examination could not be done at screening, an effort will be made to perform the examination before start of continued treatment period (at week 0 of the continued treatment, clinic visit 9). The examination will then be repeated at week 24 in the continued treatment period and thereafter every 6 months until end of treatment.

6.3 Specimen collection at patient's homes

The collections of faeces will be performed by the patients either in their home environment or at the clinic, and should be performed according to Table 4: Schedule of assessments – the first 14 weeks of the study, Table 5: Schedule of assessments – continued treatment Year 1 and 2 and Table 6: Schedule of assessments – continued treatment Year 3. The sponsor will provide collection kits and a Patient Handbook describing the collection procedures. The delivery of collection kits to patients' homes and pick-up of collections, if applicable, will be done by a courier.

